## **Funder**

Imperial Biomedical Research Centre, Institut Merieux Research Grants, EPSRC EMBRACE pump priming award.

This protocol describes the IC REACT study and provides information about procedures for entering participants. Every care was taken in its drafting, but corrections or amendments may be necessary. These will be circulated to investigators in the study. Problems relating to this study should be referred, in the first instance, to the Chief Investigator. This study will adhere to the principles outlined in the NHS Research Governance Framework for Health and Social Care (2nd edition). It will be conducted in compliance with the protocol, the Data Protection Act and other regulatory requirements as appropriate.

## **GLOSSARY OF ABBREVIATIONS**

POC	Point of care
DSS	Decision support system
AMR	Antimicrobial resistance
AMS	Antimicrobial stewardship
PCA	Principle component analysis
PPI	Patient and public involvement
AE	Adverse event
SAE	Serious adverse event
PIL	Participant involvement leaflet

## **KEYWORDS**

Antimicrobial resistance

Closed-loop control

Microneedle array

Pharmacometrics

Page 5

MISBL

V4.0 IRAS: 236047

06/12/2017

## STUDY SUMMARY

TITLE	Minimally Invasive Sensing of Beta-Lactam Antibiotics
DESIGN	Evaluation of a microneedle array device for the monitoring of beta-lactam antibiotics
AIMS	Evaluate the effectiveness of a minimally invasive microneedle biosensor for monitoring antibiotic concentrations in humans.
OUTCOME MEASURES	1) To investigate whether a microneedle biosensor can be used to monitor beta-lactam antibiotic concentrations in humans
POPULATION	(i) Healthy volunteers
DURATION	2 years

[figure not shown]
# 1. INTRODUCTION

## 1.1 BACKGROUND

Antimicrobial chemotherapeutic agents are drugs which kill or inhibit the growth of micro-organisms. Whilst essential to modern medicine, the exposure of micro-organisms to antimicrobial agents also drives generation of resistant strains, termed antimicrobial resistance (AMR). This, combined with a paucity of new antimicrobial drug development, has led to AMR becoming a global threat to modern medicine and a leading patient safety issue .

To address the challenge of AMR, it is imperative that the current finite pool of antimicrobial agents is optimised, maximising therapeutic success whilst minimising emergence of resistance . One avenue to optimise the use of antimicrobials is to ensure correct dosing strategies. Population pharmacokinetic (PK) modelling was developed from the simple concept of dose-response relationships in the 1960's . More recently the idea of individualised dosing, which accounts for intra- and inter-individual variability in PK parameters, has gained popularity and has been demonstrated to improve patient outcomes in secondary care settings (J. A. Roberts et al., 2014). In tandem to optimisation of therapy through individualising dosing, population PK modelling also allows for the consideration of individualised therapeutic drug monitoring (TDM) protocols to help provide robust and accurate data to drive individualised dosing regimens.

Currently in the UK, TDM is routinely performed for aminoglycosides and glycopeptide antimicrobial agents, given fears over the narrow therapeutic window of these agents and the serious adverse events associated with toxicity. However, in critical care the role of TDM for optimisation of therapy has been demonstrated to help optimise dosing of patients who tend to have variable pharmacokinetic parameters (J. A. Roberts *et al.*). This is of growing importance given that low concentrations of antimicrobial agents, below a micro-organisms minimum inhibitory concentration (MIC) is believed to be a major driver of AMR.

**Figure.** Concepts of therapeutic drug monitoring between different antimicrobial agents  
  
From: J. A. Roberts *et al* 2010

Moreover, in individuals managed with enhanced TDM protocols and individualised dosing protocols there is evidence that this enhances patient outcomes and reduces the cost of care for these patients, reducing hospital stay and lengths of therapy. Whilst, most evidence in this field currently focuses primarily on critical care setting, there is evidence to suggest that optimisation of therapy in secondary care can impact significantly on AMR in critical care. However, this must go beyond simply selecting the optimal antibiotic for the organism in question. We must also ensure that the optimal dose is selected to maximise micro-organism killing, whilst minimising the risk of toxicity or development of AMR. The observation of wide variability in therapeutic levels of antimicrobials being delivered to patients across a number of settings (e.g. ICU, obese, paediatric) has promoted the idea of individualised dosing that accounts for intra- and inter-individual variability in PK parameters. This has been demonstrated to improve target attainment and outcomes in secondary care (J. A. Roberts et al., 2014). To address the challenges of AMR and rapidly improve the use of antimicrobials in clinical practice, urgent validation of novel methods for precision prescribing and delivery of antimicrobial agents is required.

## 1.2 RATIONALE FOR CURRENT STUDY

Bacteria and other microorganisms can cause infections in people outside of hospitals and also among patients admitted to hospital. The antimicrobials (drugs that kill or stop the growth of microorganisms including bacteria, thereby treating infections) commonly used to treat infections are becoming less effective over time as bacteria develop resistance to them. Antimicrobial usage itself can lead to development and spread of antimicrobial resistance.

Antimicrobial resistance is now a major threat to patient safety - increasingly we are seeing patients infected with bacteria for which there are very few antimicrobials that remain effective. If untreated, these infections can be fatal in some patients. To conserve the effectiveness of antimicrobials we need to develop ways to use them more effectively. One way to do this is ensure that we are providing the best dose (amount of drug) of an antimicrobial to kill the organism causing infection, whilst also ensuring that we don't cause toxic side effects or promote the growth of antimicrobial resistance through giving too much or too little of a treatment.

Currently we give most antibiotics in a (almost) one-size-fits-all way. However, everyone is different. This includes how our bodies process and excrete antibiotics. This can even change for the individual depending on how unwell you they are. There is evidence that shows that our current approach to giving antibiotics means that some people are not treated effectively, potentially leading to development of antimicrobial resistance, side effects, or even failure of treatment.

We aim to investigate a small sensor that sits just beneath the skin to detect the amount of antimicrobial within a patient's body. By linking this to a computer dosing algorithm we can adjust the amount dose of antimicrobial given to a patient ensuring that we give the optimal amount to kill bacteria, whilst preventing any of the harmful consequences that may occur due to inappropriate therapy.

Microneedle technology was developed in the 1980's. Since then it has been applied to a number of different fields, including for the sensing of glucose levels in patients with diabetes as well as a mechanism for drug and vaccine delivery.

Despite this, its role for the monitoring of antibiotic concentrations in patients has never been explored. Below the initial layer of the skin is an area called the dermal interstitial compartment. This compartment does not have blood vessels or nerves, but does contain interstitial fluid. This interstitial fluid is in equilibrium with capillary blood, meaning that it contains metabolites, proteins and drugs within the patients system. This includes antibiotics. This offers an opportunity to be able to detect the concentration of antibiotic within the interstitial fluid without having to take blood samples from the patient. Evidence provided by Roberts and

[figure not shown]
colleagues already supports the mirrored PK profiles observed between free antibiotic levels in both the plasma and extra-cellular compartment (evaluated using microdialysis).

At Imperial College, we have developed a number of microneedle biosensors based on enzyme and aptamer based technology, that are able to detect changes in antibiotic concentrations at the levels expected in the interstitial fluid. This has been validated in the laboratory and is now ready for testing in human participants. The specific microneedle structure has been tested in healthy volunteers and type 1 diabetics as part of a separate study monitoring glucose. It has been demonstrated to be safe and effective.

This study aims to test the ability of a sensor that can monitor beta-lactam antibiotic concentrations in participants who will be given a beta-lactam antibiotic as a proof-of-concept and to allow further refinement of the sensor before progressing to test it on patients. commercial antimicrobial assays; and limited clinical data to support dose changes based on certain targets for therapy (such as trough levels or pharmacokinetic - pharmacodynamic indices).

To address these problems a potential solution is to explore the use of minimally invasive biosensors linked to closed loop control systems, which will be addressed during this research study. This follows evidence supporting the equilibrium on free antimicrobial drug PK between the plasma and interstitial fluid, which may allow for tracking plasma PK.

This study aims to translate an antibiotic biosensor, mounted on a microneedle device that has been demonstrated as safe and effective in previous human studies in diabetes. Demonstration of efficacy will allow this to be linked to a closed loop control system in the future. This has already been demonstrated to be effective in delivery of insulin for the management of diabetes and for delivery of intravenous and inhaled anaesthetic agents.

## 2. STUDY OBJECTIVES

**The principle objectives of this study are:**

1) To investigate whether a microneedle biosensor can be used to monitor beta-lactam antibiotic concentrations in humans

**The secondary objectives are:**

(i) To determine the accuracy of an antibiotic microneedle biosensor compared to gold standard plasma drug concentration sampling.

### 3. STUDY DESIGN

This study is an in-house feasibility study of a microneedle biosensor and closed loop control algorithm developed within Imperial College London.

#### OUTLINE OF THE STUDY:

This study will comprise the recruitment of 10-15 healthy volunteers. They will be recruited to test the microneedle biosensors and undergo rich plasma sampling with or without tissue microdialysis to calibrate the microneedle biosensor and evaluate its accuracy against current gold standards (i.e. plasma drug concentration and tissue microdialysis).

This study will take place at Imperial College Clinical Research Facility

#### PATIENT IDENTIFICATION:

Healthy volunteers will be recruited from a healthy volunteer database held within Imperial College London and via identification of participants within the College. An initial advertisement email will be sent and individuals responding will then followed up by telephone and invited to attend a screening visit at the Imperial CRF. They will be sent the participant information leaflet in advance of this meeting to give them time to consider the information. At this visit a member of the research team will go through the study procedure and answer any questions that the participant has.

#### CONSENT PROCEDURE:

For healthy volunteers who wish to participate in the study after considering the participant information leaflet, a trained researcher will complete the eligibility screening and gain consent for the participant to be enrolled in phase I of the clinical study.

#### STUDY METHODOLOGY:

10-15 healthy volunteers will be invited to participate in an exploratory study of the sensor device. On their screening visit the patients full blood count, renal function, liver function, and C-reactive protein will be performed to ensure that the participant is not anaemic and has no evidence of current infection. Before the study day the participant will be required to take 5 doses of oral penicillin to ensure that they are at steady state and to allow for stabilization of tissue distribution.

On arrival at the study centre the participant will have a microneedle biosensor sited for upto 12 hours.

The sensor will be sited peripherally (on an arm or leg). In a small number of cases the sensor may be sited centrally on the torso. These sensors are connected to potentiostat devices that record data, which can then be downloaded onto a computer for analysis.

Following arrival on the study day and placing of the sensor devices, a cannula will be sited for phlebotomy and a baseline beta-lactam antibiotic concentration will be taken.

A microdialysis fibre will also be inserted peripherally into tissue close to the microneedle device.

Once baseline samples have been collected the participant will receive a final dose of penicillin.

The participant will then undergo rich plasma drug concentration sampling with up to 15 further blood tests taken over a 6-12 hour period. Each blood test will involve the collection of 3ml extra blood (1 teaspoons) via a cannula which will be cited on commencement of the study. Microdialysis may be performed in a number of cases as a gold standard for determining tissue drug concentrations. Participants will also be required to complete a visual analogue scale every hour testing their level of discomfort due to the microneedle sensor device.

Time points for the blood sampling are planned to initially be taken at (0, 15, 45, 30, 60, 90, 120, 150, 180, 210, 240, 360, 480, 600, 720 minutes). However, following initial PK analysis a D-optimal design will be employed using pmetrics and bestdose pharmacokinetic software to determine the optimal time points for blood PK analysis.

Clinically relevant data including demographic, co-morbidity, and medication data will be collected by members of the research team from the participant.

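### Does the 12-hour sensor wear end before the 720-minute blood sample can be paired with it?

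*Protocol*

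**What the plan says.** All the timings are in the Protocol, Section 3, Study Methodology, in this order.

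- Siting and wear: "On arrival at the study centre the participant will have a microneedle biosensor sited for upto 12 hours".
- Cannula and baseline sample: "Following arrival on the study day and placing of the sensor devices, a cannula will be sited for phlebotomy and a baseline beta-lactam antibiotic concentration" is to be taken.
- Microdialysis: "A microdialysis fibre will also be inserted peripherally into tissue close to the microneedle device". A later sentence makes microdialysis optional.
- Dose: "Once baseline samples have been collected the participant will receive a final dose of penicillin".
- Sampling: it then lasts between 6 and 12 hours, with at most 15 samples beyond baseline. The initial times are "0, 15, 45, 30, 60, 90, 120, 150, 180, 210, 240, 360, 480, 600, 720 minutes".
- Revision: "following initial PK analysis a D-optimal design will be employed" to choose later sampling times for the blood pharmacokinetics.

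Section 2 gives the secondary objective that uses both data streams: "To determine the accuracy of an antibiotic microneedle biosensor compared to gold standard plasma drug concentration sampling". Section 7 adds a pharmacokinetic analysis of the plasma data.

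The text does not define time 0, does not give a set-up time and does not state a rule for removing the sensor. The summary of study participation announced just before Section 4 has no readable content in the text reviewed, so little weight can be placed on the absence of a timeline.

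**The concern.** Sensor wear and blood sampling have the same stated maximum, 12 hours, but they do not start together. The sensor goes on first, and the blood clock starts either at the baseline sample or at the dose, both of which come later. Two periods of equal length with staggered starts cannot end together, so on a literal reading the sensor is removed before the last blood sample is drawn.

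The secondary objective compares sensor with plasma. A plasma value without a simultaneous sensor value gives no direct comparison, and a reading that was never taken cannot be recovered at analysis. Late sampling is also thin: after 240 minutes the list has only 360, 480, 600 and 720, so losing the last removes one of four late points. In a study of 10 to 15 volunteers, each paired reading has some value.

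**Working it through.** **Inputs (Protocol, Section 3, Study Methodology).** Maximum wear is 12 h = 720 min. The initial list has 15 times, the largest being 720 min = 12 h, which agrees with the upper end of the 6 to 12 hour sampling period. The time from siting to time 0, called *s*, is not stated and is treated as an assumption.

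**Rule.** If wear is exactly 720 min counted from siting, a blood sample at time *t* has a concurrent sensor reading only when *s* + *t* ≤ 720, so the last covered time is 720 − *s*.

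| Assumed *s* (min) | Last covered time (min) | Listed times lost | Listed times paired |
|---|---|---|---|
| 0 | 720 | none | 15 of 15 |
| 15 | 705 | 720 | 14 of 15 |
| 30 | 690 | 720 | 14 of 15 |
| 60 | 660 | 720 | 14 of 15 |
| 120 | 600 | 720 | 14 of 15 |
| 180 | 540 | 600 and 720 | 13 of 15 |

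14/15 = 93.3% and 13/15 = 86.7%. The stated order of steps excludes *s* = 0, so on this strict reading at least the 720-minute sample is unpaired, whether time 0 is the baseline sample or the dose. Losing the 600-minute sample as well requires set-up longer than 720 − 600 = 120 min, and nothing in the protocol suggests that. Wear shorter than the maximum would lose more.

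**Alternative readings.**

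- Wear counted from the dose, with time 0 at the dose: the limit is 720 min and the last sample is at 720 min, so all 15 are covered.
- Wear counted from the dose, with time 0 at the baseline sample: the last sample comes before 720 min after the dose, so all 15 are covered.
- Twelve hours as a round figure for a study day: covering the full list needs 720 + *s* min of wear. That is 12.25 h for *s* = 15, 12.5 h for *s* = 30 and 13 h for *s* = 60.
- Sampling that stops at 6 hours (360 min): covered for any *s* up to 720 − 360 = 360 min.

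**Denominator.** If time 0 is the baseline sample, the list holds baseline plus 14 further samples, within the stated maximum of 15. If time 0 is separate from baseline, there are 16 samples in all, and losing the last leaves 15/16 = 93.75% paired. The result barely moves.

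**The case for a change.** The best argument for a change is that the inconsistency is certain on the literal text and cheap to remove. The wear figure is worded as a ceiling. Staff following it would have to either exceed it to cover the 720-minute sample or take the sensor off and lose the pair, and the protocol does not say which. The later optimal-design step is aimed at blood pharmacokinetics, so the new times need not respect the wear limit. Wear, time 0 and sampling times are matters of study conduct, which an analysis plan cannot repair afterwards.

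Most of this stands as description. The order of steps is as claimed, time 0 is undefined in the text, and the arithmetic is correct for any positive set-up time.

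What does not stand is the step from there to a flaw in the plan. The two 12-hour figures are matching round upper bounds for one study day, and the protocol states no removal rule and no technical or safety reason for a cut-off at minute 720. The start of the 12 hours is open enough that another reading loses nothing. The accuracy objective asks for comparison with plasma sampling and does not require every blood sample to be matched. An unpaired late sample is still used, because it informs the pharmacokinetic analysis. Revised sampling times would be chosen by the same team that sites the sensor.

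**Conclusion.** No change follows. On the strictest reading, a participant sampled to 720 minutes loses one paired time of 15, and 14 (93.3%) remain. This assumes wear at its full 12 hours and set-up of no more than 120 minutes. On the other readings nothing is lost. The number of participants kept to the initial list for the full 12 hours is not given, so no study-wide total can be stated.

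One unpaired point at the end of the curve does not bias the comparison of sensor with plasma, and it does not alter what this exploratory study can conclude. When time 0 falls and when wear begins are practical details that the team would fix in running the study day.

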#### SAMPLE ANALYSIS:

All blood samples will be put straight on ice following draw and aimed to be spun down and frozen within 2-3 hours of collection. Samples should be allowed to clot for 15-20 minutes and then centrifuged at 2,400rpm for 10 minutes. Serum from each sample will be separated into two to three vials and stored at -80°C. These will be stored on the 8th floor of the Commonwealth Building at Hammersmith Hospital Campus.

Beta-lactam concentrations will be measured using validated high-performance liquid chromatography methods.

[figure not shown]
Consent will be gained for samples to be used for calibration of electrochemical sensors in ex-vivo studies. Ideally primary analysis for the study should be completed within 90 days of collection.

#### PENICILLIN PRESCRIBING

Upon prescription of penicillin for the study, this will be provided by the pharmacy department at Imperial College Healthcare NHS Trust. In advance of the study, the finalized ethics and study protocol will be provided to the pharmacy department for approval.

Upon enrollment of participants into the study a prescription will be written for penicillin by a physician within the research team, who has assessed the patient for inclusion in the study and obtained consent. This will then be dispensed by the pharmacy department.

## Summary of study participation

## 4. PARTICIPANT ENTRY

### 4.1 RECRUITMENT

Healthy volunteer identification:

An email will be sent advertising the project to a healthy volunteer database kept within Imperial College. Furthermore, this email will be circulated internally within the college. If volunteers express an interest they will then be contacted by a member of the research team by phone to arrange a screening meeting. At the same time a copy of the patient information leaflet will be emailed to the volunteer to allow them time to consider the information prior to the screening visit.

### 4.2 INCLUSION CRITERIA

HEALTHY VOLUNTEER INCLUSION CRITERIA

- Adult >18 years old
- Healthy adults, with no evidence of active infection
- Previously received penicillin with no adverse effects

### 4.3 EXCLUSION CRITERIA

HEALTHY VOLUNTEER EXCLUSION CRITERIA

- High risk of skin soft tissue infection or local skin and soft tissue infection near sensor site
- Previous history of allergies to adhesive strips or active dermatitis
- Penicillin allergy or previous adverse event whilst receiving penicillin
- Anaemia defined as <13 g/dL in males and <12 g/dL in females

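### Women may enrol in a six-dose, non-therapeutic penicillin study, but no listed criterion excludes pregnancy or breastfeeding and no listed screening test detects pregnancy

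*Protocol*

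**What the plan says.** Section 4.2 has three inclusion criteria: age above 18 with no upper limit, good health without active infection, and penicillin tolerated in the past. Section 4.3 has four exclusions: skin or soft tissue infection (or high risk of it), adhesive allergy or dermatitis, a previous reaction to penicillin, and "Anaemia defined as <13 g/dL in males and <12 g/dL in females".

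Under Study Methodology, the bloods at the screening visit are "full blood count, renal function, liver function, and C-reactive protein will be performed to ensure that the participant is not anaemic". Their whole purpose is given as "to ensure that the participant is not anaemic and has no evidence of current infection".

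On dosing, the same section says "Before the study day the participant will be required to take 5 doses of oral penicillin" and, for the study day, "Once baseline samples have been collected the participant will receive a final dose of penicillin". On size, the Outline of the Study says "This study will comprise the recruitment of 10-15 healthy volunteers".

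Two people check eligibility. Under Consent Procedure, "a trained researcher will complete the eligibility screening and gain consent for the participant to be enrolled". Under Penicillin Prescribing, the prescription is written by a research physician "who has assessed the patient for inclusion in the study and obtained consent".

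**The concern.** A separate haemoglobin limit for females only makes sense if women can take part, and nothing restricts their age beyond being over 18. The lists nevertheless say nothing about pregnancy, breastfeeding or childbearing potential, and the screening tests look only for anaemia and infection.

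The volunteers have no infection to treat. They gain no treatment benefit from the penicillin, the antibiotic sensor or the possible microdialysis. Section 1.2 describes the antibiotic sensor as validated in the laboratory and now ready for human testing, although the microneedle structure itself had been used before in volunteers and in people with type 1 diabetes. With no benefit to set against even a small or unknown risk to a fetus or infant, the usual precaution is a written exclusion.

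What is at stake is who gets dosed. Neither study objective is threatened, and no effect on sensor calibration or accuracy is claimed.

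**Working it through.** The protocol states no figure on this point, so the check is a reading of the eligibility, screening and dosing text, with simple counts.

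**1. Are women eligible?** Yes. Section 4.3 sets a female haemoglobin limit, section 4.2 sets only a lower age limit, and no criterion restricts sex.

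**2. Does any criterion cover pregnancy or breastfeeding?**

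| Criterion | Section | Names pregnancy or breastfeeding? |
|---|---|---|
| Age above 18 | 4.2 | No |
| Healthy, no active infection | 4.2 | No |
| Penicillin tolerated before | 4.2 | No |
| Skin or soft tissue infection, or high risk of it | 4.3 | No |
| Adhesive allergy or dermatitis | 4.3 | No |
| Penicillin allergy or earlier adverse event | 4.3 | No |
| Anaemia, by sex | 4.3 | No |

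Count: 3 + 4 = 7 criteria, of which 0 apply. A requirement to be healthy does not by itself rule out a healthy pregnant or breastfeeding woman.

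**3. Would the listed tests detect pregnancy?** The tests are full blood count, renal function, liver function and C-reactive protein. That is 4 tests, of which 0 detect pregnancy.

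**4. How much dosing follows?** 5 doses before the study day + 1 on it = 6. Five of the six are taken before the study day, so a check made on that day would come too late for most of the exposure.

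**5. Does any other step close the gap?**
- The researcher's eligibility screening and the physician's assessment could exclude a declared pregnancy by judgement. The criteria they apply do not require it.
- Section 8.2 lets the clinician depart from protocol treatment, but only after entry, and only knowledge of the pregnancy would prompt it.
- Section 5.1 counts a congenital anomaly or birth defect as a serious adverse event. This is probably standard wording and is not an eligibility rule. Section 6 ends follow-up with the five-day study period.

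None of these steps requires exclusion or detects an unrecognised pregnancy.

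**6. How likely is a case?** The protocol gives neither the number of women nor a pregnancy rate, so this is an illustration on assumed inputs. With n women of childbearing potential, each with probability p of an unrecognised pregnancy, the chance of at least one is 1 − (1 − p)^n.
- n = 5, p = 0.1%: 1 − 0.999^5 = 0.5%
- n = 8, p = 1%: 1 − 0.99^8 = 7.7%

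This is a chance of exposure, not of harm. The roughly fifteenfold range reflects the assumptions alone.

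**The case against.** The strongest reply is that the protocol contains no false or contradictory sentence here. The haemoglobin line is sound, and the point concerns an absent line. Nor does the protocol say that a short oral penicillin course, the sensor or microdialysis is hazardous in pregnancy or lactation, so the need for exclusion rests on precaution and convention. Breastfeeding is the weaker half, since a pregnancy test would not detect it. Three filters precede dosing: researcher screening, the health criterion and the physician's assessment. They would probably catch a known pregnancy. The Summary of Study Participation has a heading but no content in the text available, and the information leaflet and some pages are not shown. Any of these could mention pregnancy.

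Part of this stands. The case is precautionary, the probability range is not evidence of importance, and the generic adverse event wording adds little. The unseen material limits the claim about testing more than the claim about the criteria.

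The core is not answered. Eligibility is protocol content and is not normally left to a statistical analysis plan. Sections 4.2 and 4.3 appear complete, and leaflet wording would not amend them. The protocol writes down other precautions, such as adhesive allergy and dermatitis, and does not leave those to judgement. The three filters cannot catch a pregnancy that is unrecognised or undeclared.

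**Conclusion.** The concern holds. Followed as written, the protocol would allow a pregnant or breastfeeding woman to be enrolled and given six non-therapeutic penicillin doses. In size: 0 of 7 criteria and 0 of 4 listed tests address pregnancy, in a study of 10-15 volunteers. The chance of a case is probably low and cannot be computed from the protocol.

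This is a participant-safety gap that should be corrected. It does not undermine the study's scientific aims. Confidence is medium. The conclusion assumes that the lists in 4.2 and 4.3 are complete as shown, and that the unseen participation summary adds no pregnancy test.

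**What to change.** Add pregnancy and breastfeeding as an exclusion in section 4.3. Breastfeeding has to be asked about at eligibility screening, because no blood test will show it. For women of childbearing potential, add a pregnancy test to the screening bloods under Study Methodology, and require the result before the first of the five pre-study doses is dispensed. The existing prescribing and pharmacy step is the natural place for that check.

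The cost is one line of text and one inexpensive assay on blood already drawn, with no extra visit. Eligibility narrows slightly. The test shows status at screening only.
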